9.2.1.1 Primary efficacy analysis

The primary efficacy endpoint is the percent change from Day 1 to Day 84 in LDL-C. Co-primary endpoints include the percent change from Day 1 to Day 84 in LDL-C for the obicetrapib 10 mg + ezetimibe 10 mg FDC treatment group compared with each of the following: placebo, ezetimibe 10 mg monotherapy, and obicetrapib 10 mg monotherapy, and for the obicetrapib 10 mg monotherapy treatment group compared with placebo. The primary endpoint

will be analyzed using an analysis of covariance (ANCOVA) model with a fixed effect for the treatment group and a covariate of baseline LDL-C. The least squares (LS) mean, standard errors, and 2-sided 95% confidence intervals for each treatment group and for the mean difference compared to placebo will be obtained.

Each of the comparisons within the co-primary endpoint family will be conducted at a significance level of 0.05. If and only if all 4 testing achieve statistical significance, the study is claimed to meet its primary objective and the hypothesis testing will continue to secondary endpoints, otherwise all statistical comparisons for secondary endpoints are considered descriptive only.

The primary estimand will correspond to a treatment policy estimand. The target population will comprise participants who are randomized into the study. The primary summary measure to assess the treatment effect will be the LS mean difference for the primary endpoint between obicetrapib 10 mg + ezetimibe 10 mg FDC treatment and placebo, ezetimibe 10 mg monotherapy, and obicetrapib 10 mg monotherapy based on the ANCOVA methodology. The primary estimand will be addressed using the in-study observation period (ie, including data collected post treatment discontinuation or post prohibited medication use).

Missing data will be imputed for the primary efficacy analysis based on a pattern mixture model that uses a multiple imputation technique analyzed with ANCOVA with pre-specified fixed factors and covariates. If appropriate, based on the number of retrieved dropouts, missing measurements of non-retrieved dropouts will be modeled by known measurements from retrieved dropouts (ie, participants who remain in the study after treatment discontinuation) in the same treatment group. The imputation model will be further clarified in the SAP.

Additional sensitivity analyses may be carried out under secondary estimands and/or various assumptions for missing data. Full details will be provided in the SAP.

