3.4.1 Primary Efficacy Endpoints

Primary Analysis

The primary efficacy endpoint is the percent change from Day 1 to Day 84 in LDL-C. Co-primary endpoints include the percent change from Day 1 to Day 84 in LDL-C for the obicetrapib 10 mg + ezetimibe 10 mg FDC treatment group compared with each of the following: placebo, ezetimibe 10 mg monotherapy, and obicetrapib 10 mg monotherapy, and for the obicetrapib 10 mg monotherapy treatment group compared with placebo.

Each of the comparisons within the co-primary endpoint family will be conducted at a significance level of 0.05. If and only if all 4 testing achieve statistical significance, the study is claimed to meet its primary objective and the hypothesis testing will continue to secondary endpoints, otherwise all statistical comparisons for secondary endpoints are considered descriptive only.

The LDL-C values measured by preparative ultracentrifugation (PUC) will be used. If the later measurement is not available, the LDL-C values will be assumed missing.

All the analysis for primary efficacy endpoint will be repeated with LDL-C values calculated as follows:

- 1. LDL-C will be calculated using the Friedewald equation unless triglycerides ≥400 mg/dL or LDL-C ≤50 mg/dL; where, LDL-C level will be measured directly by PUC.
- 2. LDL-C will be calculated using the Martin-Hopkins equation unless triglycerides ≥400 mg/dL or LDL-C ≤50 mg/dL; where, LDL-C level will be measured directly by PUC.

Primary Estimand

To assess the primary efficacy endpoint, the primary estimand is defined by the following key attributes:

- **Treatment**: obicetrapib 10 mg + ezetimibe 10 mg FDC treatment versus placebo, ezetimibe 10 mg monotherapy, and obicetrapib 10 mg monotherapy, and obicetrapib 10 mg monotherapy versus placebo
- Target Population: participants who are randomized into the study
- **Analysis Population**: The ITT Population
- Intercurrent events: treatment discontinuation, prohibited medication use

- **Analysis set and handling of intercurrent events**: Treatment policy strategy will be used. All available values of LDL-C at Baseline and Day 84 will be included in the calculation of the percentage change from Baseline to Day 84.

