- **Population level summary**: The difference in LS mean percentage change in LDL-C from Baseline to Day 84 between obicetrapib 10 mg + ezetimibe 10 mg FDC treatment versus placebo, ezetimibe 10 mg monotherapy, and obicetrapib 10 mg monotherapy, and obicetrapic 10 mg monotherapy versus placebo

The analysis of covariance (ANCOVA) model with a fixed effect for the treatment group and covariates of Baseline LDL-C will be used to analyze the primary efficacy endpoint. The least squares (LS) mean, standard errors, and 2-sided 95% confidence intervals for each treatment group and for the treatment comparison (FDC treatment – placebo, FDC treatment – ezetimibe 10 mg, and FDC treatment- obicetrapib 10 mg, and obicetrapib 10 mg - placebo) will be provided. Model diagnostics for the ANCOVA model will be computed that include assessment for homogeneity of variance, normality of the residual, and residual outliers. If substantial deviations from the model assumptions are observed, then supportive analyses, such non-parametric assessments, will be considered.

Missing data will be imputed for the primary efficacy analysis based on a pattern mixture model that uses a multiple imputation technique analyzed with ANCOVA with pre-specified fixed factors and covariates. If appropriate, based on the number of retrieved dropouts, missing measurements of non-retrieved dropouts will be modeled by known measurements from retrieved dropouts (i.e., participants who remain in the study after treatment discontinuation) in the same treatment group. If the number of retrieved dropouts is such that the model convergence is questionable and the given parameter estimates cannot be obtained, then missing data at the Day 84 assessment will be estimated based on the placebo treatment group as described in subsequent sections of the SAP corresponding to the first sensitivity analysis.

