Missing data at Day 84 will be imputed using a retrieved dropout imputation model assuming the data are missing not at random (MNAR). At Day 84, the data will be split into two groups as follows: (1) all participants that did not discontinue treatment and had a non-missing value at Day 84; and (2) either participants that had a missing value at Day 84, or participants that had discontinued treatment and had a non-missing value at Day 84. For the second group, 100 data sets will be imputed. The imputation model will include LDL-C Baseline and Day 84 values, treatment group. Each data set will be combined with the first group to obtain 100 imputed data sets with no missing values at Day 84. For each imputation data set, the percent change from baseline to Day 84 will be analyzed using the ANCOVA model described above. The results of these 100 analyses will be combined to construct the treatment estimates using the parameter estimates and associated standard errors. Similarly, the difference of the adjusted treatment means will be presented with the associated standard error and two-sided 95% confidence interval. Randomly chosen seed numbers will be selected for the analysis and will be retained.

Sample SAS code is shown below:

1.1

```
Note: Missing value imputation only using participant group (2): participants that had a
missing value at Day 84, or participants that had discontinued treatment and had a non-
missing value at Day 84
TREATMENT = 0 (Placebo), 1 (Obicetrapib), 3(Ezetimibe), 4 (FDC Treatment)
LDLC BASE = Baseline LDL C value
LDLC Day84 = LDL C value at Day 84
proc mi data=LDL_C seed=382794 nimpute=100 out= LDL_C_IMP;
class TREATMENT;
monotone method=reg;
var TREATMENT LDLC_BASE LDLC_DAY84;
     ____
Note: LDL_C_IMP dataset must be merged with dataset containing participants from
group (1): participants that did not discontinue treatment and had a non-missing value at
Day 84.
Note: For each imputation dataset, the percentage change from Baseline to Day 84 will
be analyzed using an ANCOVA approach with a fixed effect for the treatment group and
covariates of Baseline LDL-C.
TREATMENT = 0 (Placebo), 1 (Obicetrapib), 3 (Ezetimibe), 4 (FDC Treatment)
BASE = Baseline LDL C value
PCHG = Percent change from Baseline to Day 84
proc mixed data= TEMP;
by imputation;
class TREATMENT:
model PCHG = TREATMENT BASE / solution cl;
Ismeans TREATMENT / cl diffs;
Note: MI Analyze to combine imputations.
proc mianalyze parms(classvar=full)=mixLSM;

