class TREATMENT;
modeleffects TREATMENT;
ods output parameterestimates=mi_LSM;
proc mianalyze parms(classvar=full)=mixDIFF;
class TREATMENT;
modeleffects TREATMENT:
ods output parameterestimates=minus_mi_DIFF;
```

The first sensitivity analysis will be performed imputing missing LDL-C values at Day 84 based on the assumption the data are MNAR using a control-based pattern mixture method. At Day 84, the data will be split into two groups as follows: (1) all participants randomized to the obicetrapib 10 mg + ezetimibe 10 mg FDC treatment, ezetimibe 10 mg monotherapy, and obicetrapib 10 mg monotherapy treatment groups that had a non-missing value at Day 84; and (2) either participants randomized to the placebo treatment group, or participants that had a missing value at Day 84. For the second group, 100 data sets will be imputed. The variables for the imputation model will consist of the LDL-C values from Baseline and Day 84. In this manner, missing data at the Day 84 assessment will be estimated from the placebo treatment group. Each data set will be combined with the first group to obtain 100 imputed data sets with no missing values at Day 84. For each imputation data set, the percent change from baseline to Day 84 will be analyzed using the ANCOVA model described above. The results of these 100 analyses will be combined to construct the treatment estimates using the parameter estimates and associated standard errors. Similarly, the difference of the adjusted treatment means will be presented with the associated standard error and two-sided 95% confidence interval. Randomly chosen seed numbers will be selected for the analysis and will be retained.

The second sensitivity analysis will be performed using the ANCOVA model from the primary analysis for the ITT Population using only observed cases with no imputation for missing data.

The third sensitivity analysis will be performed using ANCOVA model from the primary analysis for the ITT Population using the last observation carried forward (LOCF), i.e. if the Day 84 measurement is missing, then the last on-treatment measurement will be used.

Supplemental Analyses

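### When the Day 84 ultracentrifugation LDL-C is missing, the primary imputation gives participants still on study drug an off-drug or placebo value

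*SAP*

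**What the plan says.** The primary analysis uses LDL-C measured by preparative ultracentrifugation (PUC). SAP 3.4.1 states: "If the later measurement is not available, the LDL-C values will be assumed missing". Missingness is thus defined by the assay result alone, not by whether the participant is taking study drug.

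The SAP's general paragraph on missing data says: "If appropriate, based on the number of retrieved dropouts, missing measurements of non-retrieved dropouts will be modeled by known measurements from retrieved dropouts", with donors from the same arm. Retrieved dropouts are participants who stopped treatment but stayed in the study. Protocol 9.2.1.1 uses the same description ("missing measurements of non-retrieved dropouts will be modeled by known measurements from retrieved dropouts") and adds: "The imputation model will be further clarified in the SAP".

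The operational paragraph and the note in the SAS code then split the data in two. Group 1 is on-drug participants with an observed Day 84 value, and it stays out of the imputation. Group 2, the only data the model sees, is "either participants that had a missing value at Day 84, or participants that had discontinued treatment and had a non-missing value at Day 84". The code line is "var TREATMENT LDLC_BASE LDLC_DAY84", with no term for treatment status.

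The fallback applies "If the number of retrieved dropouts is such that the model convergence is questionable and the given parameter estimates cannot be obtained". It is the first sensitivity analysis, whose imputation group is "either participants randomized to the placebo treatment group, or participants that had a missing value at Day 84", with baseline and Day 84 LDL-C as the only variables.

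The primary estimand in SAP 3.4.1 is treatment policy, with treatment discontinuation and prohibited medication as the intercurrent events.

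**The concern.** A lost or unreportable PUC sample is not an intercurrent event. For a participant who is still taking the drug, treatment policy asks for the value that would have been measured, and that is an on-drug value. The operational model cannot supply one, because every on-drug Day 84 value has been moved to group 1. The fallback cannot supply one in the active arms either.

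Two things follow. The between-arm difference is pulled toward zero. In addition, a handful of retrieved dropouts must support more imputed values than they need to, which widens the standard error. The trial succeeds only if all four co-primary tests are significant, and FDC versus obicetrapib has the least margin.

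**Working it through.** **1. The plan's own figure.** Inputs from SAP 2.2.2 and Protocol 9.2.4: 95 evaluable per arm, SD 25, difference 12 points, one-sided 0.025.

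SE = 25 × √(2/95) = 3.627. Power = Φ(12/3.627 − 1.96) = Φ(1.348) = 91.1%, so the stated figure of more than 90% reproduces. At 5% dropout, 380/0.95 = 400 randomized, also as stated. The 15- and 20-point contrasts have 98.5% and over 99.9%, so the 12-point contrast decides.

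**2. Bias.** Let m be the share of each arm that is on drug with Day 84 missing, and f the share of the effect lost after stopping. The contrast shrinks by 12 × m × f. At m = 1% this is 0.12 points if all effect is lost and 0.06 if half is lost. Simulation gives 0.06 to 0.13. Through attenuation alone (f = 1), power falls from 91.1% to 90.6% at m = 1%, 89.7% at 2.5% and 88.2% at 5%.

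**3. Bias and imputation variance together.** The documents give neither the number of retrieved dropouts (donors) nor the on-drug missing rate, so the counts below are assumptions.

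- Data: 100 per arm, SD 25, mean percent change 0/−15/−7/−27 (placebo/obicetrapib/ezetimibe/FDC), and lognormal baseline (median 95 mg/dL, log-SD 0.3) truncated at 70. These means keep the planned 12-, 15- and 20-point differences. FDC versus placebo is then 27, not 30, but that test has ample margin.
- Imputation: Day 84 LDL-C on arm and baseline among donors (5 coefficients), with the residual variance drawn on donors − 5 degrees of freedom; 100 imputations, ANCOVA and Rubin's rules.
- Split: on-drug missing values are drawn from on-drug observed values using arm and baseline; discontinuers are handled as in the SAP.
- 3,000 trials per setting. Discontinuers lose all effect.

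Power for FDC versus obicetrapib with 1/2/3 on-drug missing per arm:

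| Model that runs; donors and lost discontinuers per arm | As written | With split | Gain |
|---|---|---|---|
| Retrieved-dropout; 4 and 1 | 85.6/83.9/81.2% | 86.9/86.5/86.1% | 1.3/2.6/4.9 |
| Retrieved-dropout; 3 and 2 | 82.6/79.8/76.1% | 84.9/84.8/84.3% | 2.3/5.0/8.2 |
| Placebo-based; 3 and 2 | 87.2/86.3/85.3% | 87.8/87.7/86.8% | 0.6/1.4/1.5 |

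If discontinuers keep half of the effect, the first two gains become 0.7/2.0/3.0 and 1.3/3.7/5.7 points. Across all placebo-based settings the gain is 0.3 to 2.0 points. For all four tests together with 3 donors and 2 lost, power is 78/74/68% as written and 81/81/80% with the split.

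**4. Hand check of the 8.2-point cell.** Five discontinuers and 3 on-drug missing per 100 give an expected contrast of 12 × 0.92 = 11.04 as written and 12 × 0.95 = 11.40 with the split. The simulated median SEs are 4.08 and 3.82 (3.57 with no missing data).

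- As written: Φ(11.04/4.08 − 1.96) = Φ(0.746) = 77%.
- With split: Φ(11.40/3.82 − 1.96) = Φ(1.024) = 85%.
- Bias without the extra variance: Φ(11.04/3.82 − 1.96) = Φ(0.930) = 82%.

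So roughly 2 of the 8 points come from bias and 5 to 6 from asking few donors to support more imputed values.

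**5. Sensitivity to the assumptions.** A separate simulation with arm means 0/−18/−10/−30 and other baseline assumptions gave 77.4% as written and 86.1% with the split (3 donors, 2 lost, 3 on-drug missing). A repeat under the main assumptions with 1,200 trials gave 77.6% and 86.0%.

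**The case against.** The strongest reply is that this is a chosen method. The text and the code agree that all missing values go through one conservative missing-not-at-random model, and the protocol hands the detail to the SAP. That is correct as far as it goes. A reader might infer that the SAP breaches the protocol, or that no rule exists for on-drug missing values. Neither holds: the narrative passages do not say that the model is for non-retrieved dropouts alone, and the operational paragraph does supply a rule. What remains is that the rule is wider than the description, and the estimand gives no reason to treat a lost sample as a stopped treatment.

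Second, on-drug missing values should be few. Protocol 7.1.2 plans PUC for all participants at Day 84, and SAP 3.1.2 lets an unscheduled sample replace an unreportable one. This stands, and it limits the size.

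Third, large losses come mainly from donor scarcity. With 2 donors, 3 lost and 3 on-drug missing per arm, simulated power is 55.9% as written. A reader might take that as the cost of this defect. It requires that the sponsor's discretion to set the retrieved-dropout model aside goes unused. It also assumes 6 missing per arm of 100, above the planned 5% or so, and even the split reaches only 75.3%. If the placebo-based model is used instead, the split is worth at most about 2 points.

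Fourth, a careless split can reverse the bias. Protocol 4.5 foresees loss to follow-up, where drug status may be unknown. If discontinuers lost to follow-up are counted as on drug, they receive full drug effect. With 2 lost per arm the simulated contrast was −11.74 against −11.49 with no missing data, an overstatement of 0.25 points. This objection stands in full and shapes the fix.

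Fifth, SAP 3.4.1 repeats the primary analyses with Friedewald and Martin-Hopkins LDL-C, which recovers many failed PUC assays. Those repeats and the observed-case, LOCF and MMRM analyses would show part of the problem, but none of them decides success.

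**Conclusion.** The point holds as a modest flaw in the scope of the primary imputation. As written, a participant documented as on drug with a missing Day 84 PUC value is imputed as off drug or as placebo.

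The size is a conservative bias of about 0.06 to 0.13 points of the 12-point contrast per 1% on-drug missing. The loss of power is about 0.3 to 2 points if the placebo-based model runs. It is about 1 to 8 points if the retrieved-dropout model runs with 3 or 4 donors and 1 to 3 on-drug missing per arm and discontinuers lose all effect. These figures rest on assumed counts and on treatment status being known for every on-drug missing value; where it is unknown, less can be recovered. With no on-drug value missing, the effect is nil.

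A reader might infer a risk of false-positive findings. There is none here: the contrast shrinks and its standard error grows.

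**What to change.** Before unblinding, amend SAP 3.4.1 in the retrieved-dropout model and in the version of the placebo-based model that serves as the primary fallback:

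- Impute the missing Day 84 value of a participant documented as on study drug at the Day 84 visit (for example, visit attended and no discontinuation recorded) from on-drug participants of the same arm with an observed Day 84 value. Use treatment and baseline LDL-C, as in the present model.
- Keep the retrieved-dropout or placebo-based model for participants who discontinued and for anyone whose treatment status at Day 84 is unknown, including those lost to follow-up. The split then cannot give full drug effect to unrecorded discontinuers.
- Bring the general missing-data paragraph, the operational paragraph and the SAS note into line on who is imputed from whom.

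The cost is a few lines of SAP text and SAS, and reliance on recorded treatment status. The data are already collected, and the method for known discontinuers does not change. Further imputation predictors and a numerical minimum of retrieved dropouts are optional choices for the sponsor and not part of this point.

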Supplemental analyses will be performed for the primary efficacy endpoint in order to assess any differences with the results from the primary analysis and investigate what effect, if any, protocol violations have on the trial results. In the first supplemental analysis, a mixed model for repeated measures (MMRM) approach will be utilized. The analysis will include fixed effects for treatment group, visit, and treatment-by-visit interaction, along with covariates of the Baseline LDL-C value as a continuous covariate. The restricted maximum likelihood estimation approach will be used with an unstructured covariance matrix. The LS mean, standard errors, and 2-sided 95% confidence intervals for the treatment group and for the comparison of the treatment groups (FDC treatment vs. placebo, FDC treatment vs. ezetimibe 10 mg, and FDC treatment vs. obicetrapib 10 mg, and obicetrapib 10 mg vs. placebo) will be provided. The MMRM approach will include all available assessments of percent change in LDLC from Day 1, Day 28, and Day 84. The model assumes that the data are missing at random (MAR). If any data are missing, the model will use all information from the other time points to estimate the mean treatment difference at the given time point. No imputation of missing data will be performed. The analysis will be conducted for ITT Population.

Additional supplementary analysis will be performed using the ANCOVA model from the primary analysis based on the FAS, mITT, mITT On-Treatment, and PP populations. No imputation for missing data will be performed for the analysis.

Secondary Estimand

A secondary estimand will be assessed for the primary efficacy endpoint. The secondary estimand is defined by the following key attributes:

- Treatment:

- obicetrapib 10 mg + ezetimibe 10 mg FDC treatment versus placebo,
 ezetimibe 10 mg monotherapy, and obicetrapib 10 mg monotherapy, and obicetrapib 10 mg monotherapy versus placebo
- Target Population: participants who are randomized into the study
- Analysis Population: The ITT Population
- **Intercurrent events**: treatment discontinuation, prohibited medication use
- Analysis set and handling of intercurrent events: A hypothetical strategy will be used. All available values of LDL-C at Baseline and Day 84 will be included in the calculation of the percentage change from Baseline to Day 84.

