- **Population level summary**: The difference in LS mean percentage change in LDL-C from Baseline to Day 84 between obicetrapib 10 mg + ezetimibe 10 mg FDC treatment versus placebo, ezetimibe 10 mg monotherapy, and obicetrapib 10 mg monotherapy, and obicetrapic 10 mg monotherapy versus placebo.

This hypothetical estimand represents the treatment effect of FDC treatment relative to placebo, ezetimibe 10 mg monotherapy, and obicetrapib 10 mg monotherapy, and the treatment effect of obicetrapib 10 mg monotherapy relative to placebo at Day 84 in the randomized participants had they remained on their randomized treatment for the entire planned treatment period. This estimand uses a hypothetical strategy to handle intercurrent events and is intended to provide an estimation of the achievable study treatment effect if participants take the treatment as planned. The resulting missing values (corresponding to unobserved values or excluded values following study drug discontinuation or the use of prohibited medication) will be implicitly handled by using a MMRM approach under the assumption of missing at random. The model will be similar to the MMRM approach described previously for the supplemental analysis of the primary efficacy endpoint. The supplementary analysis for the primary efficacy endpoint assessed by secondary estimand will be performed using the mITT On-Treatment populations.

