3.4.3 Exploratory Efficacy Endpoints

Similar ANCOVA models as described for the primary analyses will be used to assess in obicetrapib 10 mg + ezetimibe 10 mg FDC treatment group compared with the placebo treatment group, ezetimibe 10 mg monotherapy treatment group, and obicetrapib 10 mg monotherapy treatment group, and obocetrapib 10 mg monotherapy treatment group compared with the placebo treatment group for the following:

- Percent change from Day 1 to Day 84 in VLDL-C, HDL-C, TG, Lp(a), and sdLDL-C
- Percent change from Day 1 to Day 84 in particle numbers and size, as measured by NMR analysis, of LDL-C, HDL-C, and VLDL-C
- Percent change from Day 1 to Day 28 in LDL-C.

For the percentage change from Day 1 to Day 28 in LDL-C, the LDL-C will be calculated using the Martin-Hopkins equation unless the Triglyceride value is ≥400 mg/dL or the LDL-C value is ≤50 mg/dL; in which case, the LDL-C level measured directly by PUC will be used in the analysis. The latter approach will be used because PUC assessments are not performed at Day 28 as per the protocol, unless the conditions for Triglycerides or LDL-C described above are met at the Day 28 assessment. The analysis will be repeated using the Friedewald equation as described in the Section Error! Reference source not found. above.

The proportion of participants at Days 84 who achieved

LDL-C levels of <55 mg/dL (<1.4 mmol/L), <70 mg/dL (1.8 mmol/L), and <100 mg/dL (<2.6 mmol/L)

in the obicetrapib 10 mg + ezetimibe 10 mg FDC treatment group compared with the placebo treatment group, ezetimibe 10 mg monotherapy treatment group, and the obicetrapib 10 mg monotherapy treatment group, and obicetrapib 10 mg monotherapy compared with the placebo treatment group will be examined using logistic regression models with covariates of treatment group and respective baseline values as covariates. Odds ratio with 95% confidence intervals will be estimated.

The logistic regression model will be implemented using SAS® Proc LOGISTIC. The sample SAS code can be found below:

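### The hypothetical secondary estimand contradicts itself on which LDL-C values count; as a smaller matter, LOCF and both MMRMs draw on Day 28 without naming an LDL-C method

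*SAP*

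**What the plan says.** **Which values count.** In SAP 3.4.1, the attribute list of the secondary estimand reads: "A hypothetical strategy will be used. All available values of LDL-C at Baseline and Day 84 will be included in the calculation". The primary estimand has the same rule under the other label: "Treatment policy strategy will be used. All available values of LDL-C at Baseline and Day 84 will be included in the calculation". The text below the secondary estimand's list describes the effect had participants stayed on randomized treatment. It counts as missing, among others, "excluded values following study drug discontinuation or the use of prohibited medication", and leaves them to an MMRM under missing at random.

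**Which LDL-C method.** The primary measure is LDL-C by preparative ultracentrifugation (PUC), with the rule "If the later measurement is not available, the LDL-C values will be assumed missing". Repeats are planned: "All the analysis for primary efficacy endpoint will be repeated with LDL-C values calculated as follows", by the Friedewald and Martin-Hopkins equations, with PUC where triglycerides are ≥400 or LDL-C ≤50 mg/dL. SAP 3.4.3 says that "PUC assessments are not performed at Day 28 as per the protocol, unless the conditions for Triglycerides or LDL-C described above are met", and so specifies Martin-Hopkins for the exploratory Day 28 endpoint. Table 1, footnote m, schedules PUC for everyone only at Day 1, Day 84 and EOT.

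Three analyses in SAP 3.4.1 use Day 28 without naming a method:

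- LOCF: "if the Day 84 measurement is missing, then the last on-treatment measurement will be used".
- The supplemental MMRM: "The MMRM approach will include all available assessments of percent change in LDLC from Day 1, Day 28, and Day 84".
- The secondary-estimand MMRM, described only as similar to the supplemental one.

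**The concern.** **Estimand.** Under a hypothetical strategy, LDL-C measured after stopping drug or after prohibited medication is not a value of interest. Keeping it targets treatment policy. Two programmers working from adjacent parts of SAP 3.4.1 could build different data sets for the same estimand, and one of them would answer the primary estimand's question again.

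**Day 28.** If the primary rule on missing PUC is carried to Day 28, then, EOT samples apart, a Day 28 value exists almost only where LDL-C fell to 50 mg/dL or less, or triglycerides were high. Availability then depends on the outcome and is more frequent in the active arms, contrary to the missing-at-random assumption of both MMRMs. LOCF, which the SAP's list of changes says was added to assess robustness, would fill its gaps mainly from strong responders.

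**Working it through.** **1. Planning inputs (protocol 9.2.4, SAP 2.2.2).** SD 25, 95 evaluable per arm, 5% dropout. SE of a difference = 25 × √(2/95) = 3.63. For the smallest contrast, 12/3.63 = 3.31 and Φ(3.31 - 1.96) = 0.91, so the claim of more than 90% power reproduces. 95/0.95 = 100 per arm. None of this is disputed.

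**2. Secondary estimand.** Suppose a fraction *s* of an arm stops and is fully back at the untreated level by Day 84 (assumed). Keeping those values shrinks that arm's effect by *s* × effect.

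| Contrast (planning difference) | *s* = 5% | *s* = 10% |
|---|---|---|
| FDC vs placebo (30) | 1.5 | 3.0 |
| FDC vs ezetimibe (20) | 1.0 | 2.0 |
| FDC vs obicetrapib (12) | 0.6 | 1.2 |
| Obicetrapib vs placebo (15) | 0.75 | 1.5 |

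The table assumes the same *s* in every active arm. With only half the effect lost, each figure halves.

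**3. Who would have a Day 28 PUC value.** Take a normal percent change with SD 25, a common Day 1 value, Day 28 means equal to Day 84 means, and no triglyceride trigger (all assumed). From 100 mg/dL, reaching 50 means a fall of 50%.

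- Placebo, mean 0: Φ((-50 - 0)/25) = Φ(-2.0) = 2.3%.
- Ezetimibe, mean -10 (30 - 20): Φ(-1.6) = 5.5%.
- Obicetrapib, mean -15 as stated for the contrast with placebo: Φ(-1.4) = 8.1%. With -18 (30 - 12), it is 10.0%.
- FDC, mean -30: Φ(-0.8) = 21.2%.

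At 80 mg/dL, FDC and placebo are 38% and 6.7%; at 120 mg/dL, 13% and 1.0%.

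**4. LOCF shift, 5% of Day 84 missing at random, no EOT samples, participants with nothing to carry left missing.** Let *p* be the share from step 3, *z* its cut-point and φ the normal density. The shift in an arm mean is -0.05 × 25 × φ(*z*) / (0.95 + 0.05*p*).

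- FDC: -1.25 × 0.2897 / 0.9606 = -0.38.
- Placebo: -1.25 × 0.0540 / 0.9511 = -0.07.
- FDC minus placebo: -0.31 point.

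Simulations with varying baseline, ANCOVA adjustment and correlations of 0.4 to 0.8 gave -0.22 to -0.27 under planning effects. With larger effects (obicetrapib -45.3 and ezetimibe -15.1, from protocol 1.4 and 1.5.1; FDC -53.6 assumed) they gave -0.25 to -0.38. With on-treatment EOT PUC for everyone missing, the shift was within 0.1.

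**5. The same case with baseline carried forward (change 0) where no Day 28 value exists.** FDC: 0.05 × (1 - 0.212) × 30 - 1.25 × 0.2897 = 1.18 - 0.36 = +0.82. Placebo: 0 - 1.25 × 0.0540 = -0.07. The difference is +0.89: the sign reverses. Simulation gave about +0.7 to +1.1. SAP 3.4.1 does not say what happens to these participants.

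**6. MMRM.** In a separate simulation (100 per arm, correlation 0.6, 5% missing at random), Day 84 contrasts differed by at most about 0.2 point between triggered-only and complete Day 28 data. The Day 28 means did not survive: placebo, true change 0, was estimated at -39% to -47% across all scenarios run (5% or 15% missing).

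**The case against.** **On the estimand.** The intention is plain: the bullet says hypothetical, and the next paragraph excludes values after the events. That stands, and it makes the correction easy. It does not remove the conflict, because the sentence that defines the data says the opposite.

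**On Day 28.** A reader might infer that the PUC versions of LOCF and the MMRMs certainly use outcome-selected values. The documents do not go that far. The rule on missing PUC sits under an endpoint defined by Day 1 and Day 84, and the MMRM text names no method. What can be shown is that the source is unspecified, and that applying the primary rule produces the selection.

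A reader might also infer that LOCF is biased towards FDC. Step 5 shows that the sign depends on a rule the SAP does not give.

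Several things limit the impact, and they stand:

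- Participants who stop drug should still attend Visit 4 (protocol 4.5).
- Those who withdraw should have an EOT visit, with PUC (Table 1, footnotes c and m).
- Early termination visits on Days 57 to 98 become the Day 84 value (SAP 3.1.2).
- The calculated-LDL-C repeats have Day 28 data.

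What remains open is whether an EOT value is on-treatment. Protocol 7.2 describes taking drug after the EOT trough sample, while Table 1, footnote s, says that those who permanently discontinue no longer take it. These passages need reconciling.

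**Conclusion.** The secondary estimand is wrong as written: its attribute list and its narrative cannot both be followed. The consequence is about 1.5 points for FDC versus placebo if 5% of FDC participants stop with full loss of effect, about 0.4 of an SE. It scales with the stopping rate and the loss of effect, both assumed.

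The unnamed Day 28 source is minor. If the primary rule is applied there, the LOCF shift is about -0.2 to -0.4 point for FDC versus placebo at 5% missing. That assumes no EOT samples and participants without a value left missing. Baseline distribution, correlation and missingness are also assumptions.

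Neither part supports an inference that the trial's main conclusion is at risk. The primary imputation and the first sensitivity analysis use only Baseline and Day 84, the second uses observed Day 84 cases, and the testing hierarchy does not involve Day 28.

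**What to change.** 1. In the secondary-estimand attribute list (SAP 3.4.1), replace the sentence on available values with: *Only LDL-C values obtained before treatment discontinuation or prohibited medication use will be included.*
2. In SAP 3.4.1, state that the already planned Martin-Hopkins version (rule of SAP 3.4.3, same method at Day 1, Day 28 and Day 84) is the main version of LOCF and both MMRMs. Report the PUC versions as supportive, with PUC counts by arm and visit. PUC stays the measure for the primary analysis.
3. State whether an EOT value counts as on-treatment for LOCF, and what LOCF does when there is no on-treatment post-baseline value.

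Simply discarding the triggered Day 28 PUC values is not a good alternative. It nearly reduces the PUC LOCF and MMRM to observed cases. Under assumed response-dependent dropout of 20% in the active arms, observed cases erred by -1.3 to -2.6 points for FDC versus placebo and the PUC MMRM by -1.1 to -2.4. An MMRM with all Day 28 values stayed within 0.1, assuming no method error.

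The cost is SAP wording, with no new data or extra runs. The downside is that the Martin-Hopkins version itself switches to PUC more often in the active arms (21% of FDC against 2% of placebo at 100 mg/dL in step 3). A difference from the PUC primary result may therefore reflect method as well as missing data, and the report should say so.
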